1.1 Introduction

Arterial hypertension (HTN) is one of the most important risk factors for the progression of cardiovascular diseases and plays a crucial role in the clinical course of coronary heart artery disease (CHD), peripheral artery disease, stroke, chronic heart failure (CHF) and chronic kidney disease (CKD). According to the results of Framingham Heart Study, more than 80% of patients with HTN have additional risk factors. Lipid metabolism disorders play a key role in the development of atherosclerosis and are the most important predictors of cardiovascular complications in patients with HTN [1]. Dyslipidemia accompanied by HTN is characterized by an early development of oxidative stress, endothelial dysfunction and leads to atherosclerosis progression [2-8]. The prevalence of co-existing dyslipidemia and HTN is from 15 to 31% [9, 10]. According to M.L. Johnson et al. 30, 47 and 18% of the population have dyslipidemia and HTN , isolated HTN and isolated hypercholesterolemia respectively [11]. According to the results of EUROASPIRE III study that included more than 9 000 of participants with CHD from 22 countries including Russia, hypercholesterolemia (total cholesterol ≥ 4.5 mmol/l) was identified in 51% of all cases [12]. In Framingham Heart Study about 40% of patients with HTN had hypercholesterolemia. Co-existing significant increase of systolic BP and low density lipoprotein cholesterol (LDL-C) levels was associated with an increased risk of major CV events in a 10 year perspective [1]. It has been clearly demonstrated that for patients with a combination of dyslipidemia and HTN, 10% decrease of total cholesterol level and BP lead to 45% decrease in the risk of cardiovascular complications [13].

Benefits of combined approach to antihypertensive and lipid-lowering treatment was proven in ASCOT LLA trial. According to the design of the study patients receiving antihypertensive treatment were further randomly assigned to atorvastatin 10 mg daily or placebo. The study was stopped prematurely after a median 3.3-year follow-up because of a 36% statistically significant relative risk reduction (RRR) in non-fatal myocardial infarction and fatal CHD (the primary outcome) in favour of atorvastatin and a statistically significant RRR in fatal and non-fatal stroke (27%), total CV events (21%) and total coronary events (29%) [17]. Following the addition of atorvastatin to amlodipine-based treatment with or without perindopril, the relative risk of non-fatal MI and of fatal CHD decreased by 53% ($p < 0.001$), whereas that of all cardiovascular events and of revascularization procedures by 27% (both $p = 0.001$) after 3.3 years of treatment. By contrast, adding atorvastatin to an alternative antihypertensive combination (atenolol \pm bendroflumethiazide) did not achieve any significant reduction of these clinical endpoints [21].

Blood pressure and lipid-lowering effectiveness of a triple fixed combination of atorvastatin, perindopril and amlodipine, administered in various dose combinations, was evaluated in a 3-month , prospective, multicentre, observational, non-interventional study. After 3 months of

therapy mean office blood pressure decreased from 158.5 ± 16.7 / 91.7 ± 9.4 to 132.2 ± 8.3 / 80.1 ± 6.8 mmHg ($p < 0.0001$), whereas mean 24-h blood pressure decreased from 146.0 ± 14.5 / 82.5 ± 12.1 to 132.1 ± 13.2 / 75.6 ± 9.9 mmHg. Total cholesterol level decreased from 6.18 ± 1.15 to 5.16 ± 0.88 mmol/l and LDL-C - from 3.41 ± 1.01 to 2.80 ± 0.82 mmol/l and triglyceride level from 2.26 ± 1.17 to 1.82 ± 0.83 mmol/l (all $p < 0.0001$) [16].

According to the results of the epidemiological studies in Russia only 20% of patients with HTN achieve target level of BP and only 17.4% achieve target level of LDL-C [14,18]. Non-sufficient adherence to the prescribed antihypertensive treatment is one of the most important reasons for this finding [19]. The use of single pill combinations (SPC) has been shown to increase adherence to treatment by 29% [22]. According to Russian clinical guidelines the majority of patients with HTN require a combination dual treatment from the start. It is clearly stated that SPC should be preferred in all cases [15].

Treatment with the fixed triple combination of atorvastatin, perindopril and amlodipine might take us closer to the optimal therapy for hypertensive patients with hypercholesterolaemia. The expected improvement of patient adherence to treatment may result in an increase of the percentage of patients who achieve both blood pressure control and the LDL-cholesterol targets recommended in guidelines. Moreover, this may translate into the further decline of the risk of major cardiovascular events.

1.2 Objectives

Primary objective is to describe antihypertensive and hypolipidaemic effectiveness of a triple single-pill combination of amlodipine, atorvastatin and perindopril at 12 weeks in patients with arterial hypertension (HTN) and dyslipidemia in the daily clinical practice.

Secondary objectives

- To determine the proportion of patients who reached systolic (SBP) and diastolic blood pressure (DBP) target goals at weeks 4 and 12 of the observation period respectively.
- To determine the proportion of patients who reached LDL-C target goals at week 12 of the observation period.
- To evaluate the quality of life of patients at visit 1 (V1) and visit 2 (V2) as compared to visit 0 (V0) respectively.
- To evaluate the adherence to treatment with the fixed dose combination (FDC) of amlodipine/atorvastatin/perindopril in patients included into the study at V1 and V2 as compared to V0.
- To evaluate predictors of reaching BP and LDL-C target goals in the study population.

1.3 Study variables

Primary variables:

- Mean change from baseline (BL) in SBP and DBP assessed at week 12 of the observational period.
- Mean change from BL in LDL-C assessed at week 12 of the observational period.

Secondary variables:

- Mean change from BL in SBP and DBP assessed at week 4 of the observation period.
- Proportion of the patients aged 18-64 years who reached SBP <140 mm Hg and DBP <90 mm Hg at week 4 of the observation period.
- Proportion of patients aged 18-64 years who reached target SBP <130 and \geq 120-mm Hg and DBP between 70 and79 mm Hg at week 12 of the observation period.
- Proportion of patients older than 65 years who reached SBP < 140 mm Hg and DBP < 90 mm Hg at week 4 of the observation period.
- Proportion of patients older than 65 years who reached SBP \leq 139 and \geq 130 mm Hg and DBP between 70 and79 mm Hg at week 12 of the observation period.
- Proportion of patients at very high CV risk who reached LDL-C decrease \geq 50% from BL and reached target < 1,4 mmol/l (55 mg/dl) or at week 12 of the observation period.
- Proportion of patients at high CV risk who reached LDL-C decrease \geq 50% from BL and reached target LDL-C < 1,8 mmol/l (70 mg/dl) at week 12 of the observation period.
- Proportion of patients at moderate CV risk who reached target LDL-C < 2,6 mmol/l (100 mg/dl) at week 12 of the observation period.
- Proportion of patients at different CV risk who reached both BP and LDC-C targets
- Proportion of patients aged 18-64 years at very high CV risk who reached SBP <130 and \geq 120 mm Hg and DBP between 70 and79 mm Hg at week 12 of the observation period in the subgroups of the patients receiving SPC of amlodipine/atorvastatin/perindopril in the following dosages 5;20;5 mg and 5;20;10 mg and 5;10;5 mg respectively;
- Proportion of patients older than 65 years at very high CV risk who reached SBP \leq 139 and \geq 130 mm Hg and DBP between 70 and79 mm Hg at week 12 of the observation period in the subgroups of patients receiving SPC of amlodipine/atorvastatin/perindopril in the following dosages 5;20;5 mg and 5;20;10 mg and 5;10;5 mg respectively
- Proportion of patients at very high CV risk who reached LDL_C decrease \geq 50% from BL and reached target <1,4 mmol/l (55 mg/dl) or at week 12 of the observation period in the subgroups of the patients receiving SPC of amlodipine/atorvastatin/perindopril in the following dosages 5;20;5 mg and 5;20;10 mg and 5;10;5 mg respectively;
- Proportion of patients aged 18-64 years at high CV risk who reached SBP <130 and \geq 120 mm Hg and DBP between 70 and79 mm Hg at week 12 of the observation period in the subgroups of patients receiving SPC of amlodipine/atorvastatin/perindopril in the following dosages 5;20;5 mg and 5;20;10 mg and 5;10;5 mg respectively;
- Proportion of patients older than 65 years at high CV risk who reached SBP \leq 139 and \geq 130 mm Hg and DBP between 70 and79 mm Hg at week 12 of the observational period in the subgroups of patients receiving SPC of amlodipine/atorvastatin/perindopril in the following dosages 5;20;5 mg and 5;20;10 mg and 5;10;5 mg respectively;

- Proportion of patients at high CV risk who reached decrease of LDL-C from BL $\geq 50\%$ and reached target $<1,8$ mmol/l (55 mg/dl) at week 12 of the observation period in the subgroups of patients receiving SPC of amlodipine/atorvastatin/perindopril in the following dosages 5;20;5 mg and 5;20;10 mg and 5;10;5 mg respectively;
- Proportion of patients aged 18-64 years at moderate CV risk who reached SBP <130 and ≥ 120 mm Hg and DBP between 70 and 79 mm Hg at week 12 of observational period in the subgroups of patients receiving SPC of amlodipine/atorvastatin/perindopril in the following dosages 5;20;5 mg and 5;20;10 mg and 5;10;5 mg respectively;
- Proportion of patients older than 65 years at moderate CV risk who reached SBP ≤ 139 and ≥ 130 mm Hg and DBP between 70 and 79 mm Hg at week 12 of the observation period in the subgroups of patients receiving SPC of amlodipine/atorvastatin/perindopril in the following dosages 5;20;5 mg and 5;20;10 mg and 5;10;5 mg respectively;
- Proportion of patients at moderate CV risk who reached LDL-C $< 2,6$ mmol/l (100 mg/dl) at week 12 of the observation period in the subgroups of patients receiving SPC of amlodipine/atorvastatin/perindopril in the following dosages 5;20;5 mg and 5;20;10 mg and 5;10;5 mg respectively;
- Mean change from V0 in scores of the SF-36 questionnaire assessed at V1 and V2;
- Proportion of patients with high, moderate and low adherence to the treatment with SPC of amlodipine/atorvastatin/perindopril at V1 as compared to V0 via medication adherence scale;
- Proportion of patients with high, moderate and low adherence to the treatment with SPC of amlodipine/atorvastatin/perindopril at V2 as compared to V0 via medication adherence scale;
- Association between the fact of achieving target BP levels at week 12 and baseline BP and LDL-C levels;
- Association between the fact of achieving target LDL-C level at week 12 and baseline BP and LDL-C levels as well as CV risk category;
- Association between the fact of achieving target BP and LDL-C levels at week 12 with the categories of CV risk, initial dosage of SPC amlodipine/atorvastatin/perindopril and adherence rate to the administered therapy with FDC.
- Association between patients' adherence to SPC amlodipine/atorvastatin/perindopril therapy at week 4 and week 12 and baseline BP level.
- Predictors for achieving target BP levels (i.e. smoking, sex, baseline SBP and DBP, duration of HTN, level of CV risk, duration of therapy, baseline LDL-C level, CAD diagnosis);
- Predictors for achieving target LDL-C levels (i.e. smoking, sex, baseline SBP and DBP, duration of HTN, level of CV risk, duration of therapy, baseline LDL-C level, CAD diagnosis).

2. Methods and documentation

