Appendix 6. Categories of CV risk and target levels of LDL-C [15]

Risk	Definition	Target level of LDL-C, mmol/l (mg/dl)
Extreme	Combination of ACVD ¹ with DM 2 and/or FH or two cardiovascular complications within 2 year ² in a patient with ACVD regardless of optimal hypolipidemic therapy and/or achieved level of LDL-C \leq 1,4 mmol/l	< 1,4 (55), optimal < 1,0 (40)
Very high	
 - Documented CVD with clinical or based on instrumental findings (history of ACS, stable angina, PCI, CAPG or other interventions on the arteries, 	< 1,4 (55) or decrease from baseline \geq 50%

	
Stroke/TIA, atherosclerosis of peripheral arteries)
 
 – Clinically significant atherosclerotic plaque based on CAG/CT (stenosis \geq 50% in 2 coronary arteries) or duplex scan of carotid arteries (stenosis $>$ 50%) – DM + target organs damage + \geq 3 RF and early start of DM 1 with the duration $>$ 20 years – CKD with eGFR $<$ 30 ml/min/1,73 m² – SCORE risk \geq 10% – FH + CVD or RF 	
High	
Important RF Total cholesterol $>$ 8 mmol/l, and/or LDL-C $>$ 4,9 mmol/l and/or BP \geq 180/110 mm Hg
 
 – FH without RF – DM without target organ damage, DM \geq 10 years or with the RF – Moderate CKD with eGFR 30–59 ml/min/1,73 m² – SCORE risk 5–10% – Hemodynamically non-significant atherosclerosis of non-coronary arteries (stenosis 25–49%) 	$< 1,8$ (70) or decrease from baseline $\geq 50\%$
Moderate	
Young patients (DM 1 – younger than 35 years, DM 2 – younger than 50 years) with the duration of DM $<$ 10 years without target organ damage and RF
 
 – SCORE risk 1–5% 	$< 2,6$ (100)
Low	SCORE risk $<$ 1%	$< 3,0$ (116)

Notes: *LDL-C* – Low-density lipoprotein cholesterol; *DM* – diabetes mellitus; *FH* – familial hypercholesterolemia; *ACVD* – atherosclerotic cardiovascular disease; *CVD* – cardiovascular diseases; *ACS* – acute coronary syndrome; *PCI* – percutaneous coronary intervention; *CAPG* – coronary artery bypass grafting; *TIA* – transient ischaemic attack; *ACB* – атеросклеротическая бляшка; *CAG* – coronary angiography; *CT* – computer tomography; *RF* – risk factor; *eGFR* – glomerular filtration rate; *SCORE* Systematic Coronary Risk Evaluation.

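### LDL-C target at very high and high risk: section 1.3 requires a 50% fall and a value below threshold, Appendix 6 accepts either; four smaller mismatches in the same definitions

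*Combined protocol and SAP*

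**What the plan says.** **LDL-C proportions, section 1.3.** Four lines cover very high and high CV risk, overall and by dose. Each starts from a fall of at least 50% from baseline and then adds a threshold:

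- Very high risk, overall: "from BL and reached target < 1,4 mmol/l (55 mg/dl) or at week 12 of the observation period".
- Very high risk, by dose: "and reached target <1,4 mmol/l (55 mg/dl) or at week 12 of the observation period in the subgroups".
- High risk, overall: "and reached target LDL-C < 1,8 mmol/l (70 mg/dl) at week 12 of the observation period".
- High risk, by dose: "and reached target $<1,8$ mmol/l (55 mg/dl) at week 12 of the observation period".

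**LDL-C targets, Appendix 6.** The very-high-risk row reads "< 1,4 (55) or decrease from baseline" of at least 50%. The high-risk row has the same structure around 1.8 mmol/l (70 mg/dl). The table also has Extreme and Low classes, which have no line in section 1.3.

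**Items that say only 'target'.** One is "Proportion of patients at different CV risk who reached both BP and LDC-C targets". The others are the two association items that involve LDL-C target attainment and the LDL-C predictor item, all in section 1.3.

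**BP proportions, section 1.3.** There are five lines for ages 18-64 and five for patients older than 65. At week 12 the 18-64 lines use SBP from 120 to below 130 mm Hg. Section 2.4.1 admits patients from 18 to under 80. Appendix 7 starts its second age band at 65 and, for ages 18-64 with chronic kidney disease (CKD), gives SBP from 130 to below 140.

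**The concern.** Requiring both conditions and accepting either one are different endpoints. The two very-high-risk lines cannot settle the matter, because the stray 'or' suggests that words were lost. The two high-risk lines read clearly but contradict Appendix 6, which is the only place that sets out the risk classes used in section 1.3.

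Two of the five secondary objectives rest on these indicators: the proportion reaching LDL-C goals and the predictors of reaching goals. Section 4.2 defines no responder variable. A programmer could take the proportion tables from section 1.3 and look up 'target' in Appendix 6 for the combined, association and predictor items. One report would then hold two definitions under one name.

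The smaller mismatches are of the same kind: a threshold with two incompatible units, an age that falls in no stratum, and two SBP ranges for the same patients.

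**Working it through.** **1. What is not affected.** The LDL-C sample size in section 2.2 uses the mean change, not a responder rate. It reproduces: 1.01² × (2.326 + 1.282)² / 0.22² = 1.0201 × 13.018 / 0.0484 = 274.4, against 274 stated.

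**2. The two rules.** Let B be baseline LDL-C, W the week-12 value and t the threshold (1.4 or 1.8).

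- Both conditions: W < t and W ≤ 0.5B, so W must lie below the lower of t and 0.5B.
- Either condition: W must lie below the higher of the two.

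The rules coincide only when 0.5B = t, that is at B = 2.8 mmol/l (very high risk) or 3.6 mmol/l (high risk). Two very-high-risk examples:

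- 2.5 to 1.35 mmol/l: a fall of 46.0%, ending below 1.4.
- 4.0 to 1.9 mmol/l: a fall of 52.5%, ending above 1.4.

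Both patients fail under section 1.3 and succeed under Appendix 6.

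**3. Size, as an illustration.** Inputs from the documents: means 3.09 to 2.65 (section 2.2) or 3.41 to 2.80 (section 1.1), with SDs 1.01 and 0.82 (section 1.1). Assumed: within-patient correlation 0.3, 0.5 or 0.7; normal or log-normal values; one distribution for all risk classes. That gives 12 scenarios per threshold.

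One scenario in full (3.09 to 2.65, normal, correlation 0.5, t = 1.4):

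- Below threshold: z = (1.4 − 2.65)/0.82 = −1.524, probability 6.4%.
- Fall of at least 50%: W − 0.5B has mean 2.65 − 1.545 = 1.105 and variance 0.6724 + 0.2550 − 0.4141 = 0.5133 (SD 0.716). So z = −1.542, probability 6.2%.
- The correlation between W and W − 0.5B is (0.6724 − 0.2071)/(0.82 × 0.716) = 0.79. The bivariate normal then gives both = 3.2%.
- Either = 6.37 + 6.15 − 3.17 = 9.35%.

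All 12 scenarios:

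| Rule | t = 1.4 | t = 1.8 |
|---|---|---|
| Both | 0.1–4.1% | 0.4–6.6% |
| Threshold alone | 1.2–6.4% | 8.1–15.0% |
| Either | 2.4–11.3% | 9.0–17.4% |
| Either minus both (points) | 2.2–7.3 | 8.6–13.4 |

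Sensitivity to the SDs, using the section 2.2 means:

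- SD 1.01 (section 2.2) at both times: the difference is 6.8–9.8 points at 1.4 and 11.4–18.4 at 1.8.
- SDs rescaled to the coefficients of variation in section 1.1 (0.915 and 0.776): 2.4–6.1 and 9.8–11.7 points.

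**4. Effect on the predictor analysis.** Baseline LDL-C is a named predictor. When patients are split at the mean baseline, the direction of its association with success differs between the two rules in about half of the scenario and threshold combinations. Example (t = 1.8, 3.09 to 2.65, log-normal, correlation 0.5): both conditions, about 1% with low baseline against 3% with high; either condition, about 20% against 9%.

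**5. Units.** The LDL-C target pairs in the documents give 55/1.4 = 39.3, 70/1.8 = 38.9, 100/2.6 = 38.5, 116/3.0 = 38.7 and 40/1.0 = 40.0 mg/dl per mmol/l. The high-risk by-dose line gives 55/1.8 = 30.6, so it holds two different thresholds.

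**6. Age 65.** In completed years, '18-64' and 'older than 65' leave age 65 out of all ten age-stratified BP lines. The combined, association and predictor items carry no age limit and are not affected. If age is normal with mean 55–65 and SD 8–12 (assumed), truncated to 18–79 completed years, 2.1–5.1% of patients are aged 65. That is about 6–14 of 274.

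**7. CKD.** For ages 18-64, 120 to below 130 (section 1.3) and 130 to below 140 (Appendix 7) do not overlap. GFR below 60 is a non-inclusion criterion (section 2.4.2), so only CKD patients with GFR of 60 or more are touched, although section 4.2 plans a CKD subgroup.

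**The case against.** Section 1.3 is where the study variables are defined, while Appendix 6 is a table taken from a guideline, and the body text does not say that it governs the endpoints. An endpoint may be stricter than a guideline. On that view the high-risk lines have one answer, and the 'target' items simply reuse the definitions in their own list.

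This has force for the two high-risk lines. It does not repair the two broken very-high-risk lines. Nor does it change the fact that section 1.3 takes its risk classes from the table whose target column it contradicts. Bringing the Extreme and Low classes into the 'target' items is an inference, but the wording leaves it open.

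The percentages are also open to challenge. The documents give no LDL-C distribution by risk class, and one scenario set combines means and SDs from different sections. That an either-rule yields more responders than a both-rule is true by definition. These objections stand, so only the rough size is informative, and the span should include the wider result with SD 1.01.

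The age point depends on a strict reading of 'older than 65', and 65 and over may well be intended. The unit and CKD points are small. Finally, the analysis is descriptive and exploratory, both LDL-C values are collected, and section 4.2 plans frequency tables for composite endpoints. Every definition therefore stays computable, but none of this says which one will be reported.

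**Conclusion.** The concern holds. For very high and high risk, section 1.3 and Appendix 6 give different responder rules, and nothing in the protocol reconciles them. Under the stated assumptions (correlation 0.3–0.7, normal or log-normal, one distribution for all classes), the choice moves the reported rate by about 2–10 points at 1.4 mmol/l and 9–18 points at 1.8 mmol/l once the SD of 1.01 is included. It can also reverse the apparent role of baseline LDL-C. These figures show scale and do not predict the study's results.

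The unit mismatch, the age-65 gap and the CKD range are also in the text, but are minor. The primary variables, the sample size and the moderate-risk LDL-C lines are untouched. This should be fixed, because the reported proportions are a main product of a descriptive study.

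**What to change.** Before database lock:

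- Reconcile section 1.3 with Appendix 6, so that each LDL-C endpoint has one coded definition, used in every item that says 'target'. State how Extreme and Low risk patients enter those items.
- Complete or remove the unfinished 'or' in both very-high-risk lines.
- Tabulate the LDL-C components separately for very high and high risk: below threshold, fall of at least 50%, both, either. The result can then be read under any definition.
- Reconcile the mg/dl figure beside 1.8 mmol/l in the high-risk by-dose line with the overall line and Appendix 6.
- Reconcile the age bands with Appendix 7, so that every eligible age falls in exactly one group.
- Reconcile the 18-64 SBP range for CKD between section 1.3 and Appendix 7.

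Which target is clinically right is for the sponsor to decide. The cost is wording in section 1.3 and the appendices plus a few table rows, with no new data, visits or patients.

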According to the literature the following assumptions were made:

- Study drug efficacy (μ_A) – mean LDL-cholesterol level after 3 month of therapy will be 2.65 mmol/L.
- Null hypothesis drug efficacy (μ_0) - mean LDL-cholesterol level will be the same as at baseline – 3.09 mmol/L.
- Maximum Standard deviation (σ) – 1.01 mmol/L.
- Superiority margin (δ) considered as half of the difference between the drug and baseline – -0.22 mmol/L (*D'Agostino Sr R. B., Massaro J. M., Sullivan L. M. Non-inferiority trials: design concepts and issues—the encounters of academic consultants in statistics //Statistics in medicine. – 2003. – T. 22. – №. 2. – C. 169-186.; Food and Drug Administration et al. Non-inferiority clinical trials to establish effectiveness: guidance for industry //US Department of Health and Human Services. – 2016.; Committee for Proprietary Medicinal Products (CPMP et al. Points to consider on switching between superiority and non-inferiority //British journal of clinical pharmacology. – 2001. – T. 52. – №. 3. – C. 223.*).
- Type I error (α) – 1%. $Z_{1-\alpha} = 2,326$.
- Type II error (β) – 10%. $Z_{1-\beta} = 1.282$.

The null hypothesis is formulated as:

“Change in mean LDL-cholesterol level after 3 month of therapy comparing to baseline will be not less than -0.22 mmol/L”

$$H_0: \mu_A - \mu_0 \geq -0.22$$

The alternative hypothesis is formulated as:

“Change in mean LDL-cholesterol level after 3 month of therapy comparing to baseline will be less than -0.22 mmol/L”

$$H_1: \mu_A - \mu_0 < -0.22$$

As a result of the calculation, it was defined that in order to obtain statistically significant results, it is necessary to use data from at least 274 completed cases.

To obtain statistically significant results on all three primary endpoints the greatest value of calculated sample size was chosen – 274 completed cases.

Taking into account the possible drop-out rate of 30% of patients during the study, 400 patients should be included in the study.

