4.2 Statistical analysis

Due to the non-interventional nature of this study, statistical analysis will be carried out in descriptive and exploratory forms. All parameters will be analysed using descriptive statistics. For each parameter, the following will be specified: number of patients, mean value, standard error, minimum and maximum values, or proportion of each category. All composite endpoints will be listed and presented in visual form as graphs and in tables of parameters and their frequencies. For categorical variables, absolute values and rates in per cents be calculated. The calculations of relative rates will include only patients in whom values of the corresponding variables will be available.

Accepted level of significance

In all tests, a significance level of 0.05 will be used, and 2-sided statistical tests will be carried out.

Search statistical analysis will be performed in the following subgroups of patients:

- patients with stable CAD
- patients with diabetes mellitus type 1 or type 2
- patients with chronic kidney disease

All reports of adverse drug reactions (ARDs), adverse events (AEs), serious ADR/AE, and special situations will be encoded using MedDRA by the subcontractor, and the results will be listed and classified according to the System-Organ-Classes (SOCs). Descriptive statistics will be used.

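### As written, the adherence comparison of V1 and V2 with V0 is not confined to the same patients, so drop-out alone can move the difference

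*Combined protocol and SAP*

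**What the plan says.** Section 1.3 lists two adherence variables, one for each later visit. The V2 variable is "Proportion of patients with high, moderate and low adherence to the treatment with SPC of amlodipine/atorvastatin/perindopril at V2 as compared to V0", and the V1 variable is worded the same way. Both are class proportions at a visit; neither is a change or a transition within a patient. The matching objective in Section 1.2 concerns adherence "in patients included into the study at V1 and V2 as compared to V0" and does not restrict V0 to patients seen later.

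Other before-after variables in the same list are tied to the patient's own starting value. SF-36 is "Mean change from V0 in scores of the SF-36 questionnaire assessed at V1 and V2", and blood pressure and LDL-C are mean changes from baseline.

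Section 4.2 sets the denominator: "The calculations of relative rates will include only patients in whom values of the corresponding variables will be available". On method it says "All parameters will be analysed using descriptive statistics", with a two-sided 0.05 level for any tests. It names no test for adherence, no set of patients with both visits, and no shift table.

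Section 2.2 gives the expected loss: "Taking into account the possible drop-out rate of 30% of patients during the study, 400 patients should be included in the study". Table 1 in Section 2.7.2 schedules the adherence scale at V0, V1 and V2, so paired values will exist for patients who stay.

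**The concern.** If each visit has its own denominator, the V2 patients are a subset of the V0 patients. The observed V0-to-V2 difference then has two parts: what happened within patients who stayed, and the effect of removing those who left. The second part says nothing about change in adherence. If patients with poorer adherence at V0 are more likely to leave, the proportion with high adherence rises with no patient having changed.

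Evaluating adherence at V1 and V2 against V0 is a named secondary objective. A reader of the report could not separate the two parts from the visit proportions alone. Showing the number of patients at each visit, which Section 4.2 requires, would reveal that the denominators differ but not how much of the difference comes from that.

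**Working it through.** **Inputs from the plan (Section 2.2).** 274 completed cases, 30% possible drop-out, 400 patients included.

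**The plan's own figure.** For LDL-C, n = 1.01² × (2.326 + 1.282)² / 0.22² = 274.4, stated as 274. Inflating for drop-out gives 274 / 0.7 = 391.4, so 392, stated as 400. The figures reproduce closely enough. With 400 included, 400 × 0.7 = 280 are expected at V2. None of this sizes the adherence comparison.

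**Composition effect.** Let c and d be the V0 shares with high adherence in completers and drop-outs, and suppose nobody changes class.

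- V0 figure, all patients: 0.7c + 0.3d
- V2 figure, completers: c
- Apparent change: c − (0.7c + 0.3d) = 0.3(c − d)

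The documents give no adherence distribution, so c = 65% and the values of d are assumptions:

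| V0 share in drop-outs | Gap | V0 figure | V2 figure | Apparent rise |
|---|---|---|---|---|
| 55% | 10 points | 62% | 65% | 3 points |
| 45% | 20 points | 59% | 65% | 6 points |
| 35% | 30 points | 56% | 65% | 9 points |

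With lower drop-out the effect shrinks in proportion: for the same gaps it is 2, 4 or 6 points at 20% and 1, 2 or 3 points at 10%. The plan gives no drop-out figure for V1.

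**How this would look if tested without pairing.** This is an illustration, not a planned analysis. SE = √[p₀(1 − p₀)/400 + c(1 − c)/280]. For the 9-point case, √[0.56 × 0.44/400 + 0.65 × 0.35/280] = 3.8 points, so z = 9/3.8 = 2.4. The 6- and 3-point cases give z of about 1.6 and 0.8. Only the largest assumed gap crosses the 0.05 level.

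**Same patients at both visits.** When both proportions are taken in the same patients and nobody changes class, the apparent change is zero by construction.

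**Precision.** With no net change, the paired SE is √(share changing between high and not high / 280):

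| Share changing class | Paired SE |
|---|---|
| 10% | 1.9 points |
| 30% | 3.3 points |
| 40% | 3.8 points |

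The unpaired figure is about 3.8 points. Pairing therefore narrows the interval if 10% to 30% change class, and gains nothing at about 40% or more.

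**The case against.** The strongest objection is that the plan leaves this open and does not get it wrong. The rule in Section 4.2 refers to the corresponding variables, and the variable is a comparison of V2 with V0. Requiring both values is a fair reading, and under it the problem disappears. That stands as a possible reading, but the text does not state it, and the visit-by-visit reading is the more literal one.

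A reader might infer more than the documents support in four ways:

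- **That an unpaired test with a wrong standard error is planned.** No test is prescribed for adherence, and a paired one is not ruled out.
- **That the bias favours the product.** Its direction depends on who leaves, and the documents do not say. Section 2.4.2 excludes patients with supposed low adherence, which may narrow the gap. Appendix 2 gives no cut-offs for the three classes, so the assumed shares have no anchor in the documents.
- **That the comparison tests the adherence benefit the introduction expects from the single pill.** Under Sections 2.1 and 2.7.4, V0 adherence is already measured on the single pill. V2 against V0 shows change on treatment, not the benefit of switching to it, and pairing does not alter that.
- **That two unrelated groups are compared.** The sets are nested.

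It is also fair to say that a both-visits set describes only patients who stayed, so selection by drop-out is made visible but not removed.

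**Conclusion.** The point holds in a limited form. Applied as written, the denominator rule and the class-proportion definition give a V0-to-V2 difference that can move by 0.3 × the completer-minus-drop-out gap through composition alone. That is 3 to 9 points for assumed gaps of 10 to 30 points at the allowed 30% drop-out. The formula is exact when nobody changes class, all included patients have a V0 value and only completers have a V2 value. The gap is an assumption throughout: with no gap the effect is zero, and with a reversed gap it is negative. The gain in precision from pairing is likely but depends on how many patients change class.

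This goes somewhat beyond missing detail, because a stated rule produces the mismatch and a better comparison is available from data already scheduled.

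**What to change.** In Section 1.3, define the adherence comparisons of V0 with V1 and of V0 with V2 in patients with both values, separately for each later visit. In Section 4.2, add for each comparison:

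- a 3×3 shift table (high, moderate, low);
- the paired difference in the proportion with high adherence, with a 95% CI;
- if a test is wanted, McNemar for high versus not high, or Stuart-Maxwell for the three classes;
- V0 adherence shown separately for patients without the later value, so that any gap can be seen.

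The cost is about one sentence in each section and one extra table, with no new data collection. The small downside is that the comparison describes those who stayed; patients with only a V0 value leave it and are reported beside it. The report should describe the result as change while on the single pill.
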